### **Section 9.0 Statistics**

Due to the rarity of Cushing disease in the general population, it is difficult to do a randomized placebo controlled trial with sufficient sample size numbers to achieve adequate power. By using subjects as their own controls, we measure pre- and post-treatment changes on the same population, therefore alleviate the issues with recruitment.

We used a Simon exact single-stage phase II design (8) to determine the sample size for 80% power and a one-sided 0.05 significance level. The trial tests the null hypothesis that the seliciclib (response rate)  $\leq 5\%$  (unacceptable response rate) versus the alternative hypothesis that  $RR \geq 25\%$  (promising response rate). We enroll 16 patients. If at least 3 of the 16 respond, we conclude that seliciclib is promising in the treatment of ACTH-producing pituitary tumors.

A regression model will be used to investigate the relationship between end-of-study UFC and baseline UFC. The comparison between serum cortisol or plasma ACTH in patients who responded to seliciclib and in those who did not respond will be performed by a Student's *t* test. Categorical variables, i.e. normalization of 24 hour UFC, development of new pituitary deficits, and visual field deficits will be compared in the pre- and post- treatment time points using fisher's exact test.

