**Inclusion criteria:**

- Male and female patients at least 18 years old
- Patients with confirmed pituitary origin of excess adrenocorticotrophic hormone (ACTH) production:
  - Persistent hypercortisolemia established by two consecutive 24 hr UFC levels at least 1.5x the upper limit of normal
  - Normal or elevated ACTH levels
  - Pituitary macroadenoma ( $>1$  cm) on MRI OR
  - Inferior Petrosal Sinus Sampling (IPSS) central to peripheral ACTH gradient  $>2$  at baseline and  $>3$  after CRH stimulation
  - Recurrent or persistent Cushing disease is defined as pathologically confirmed resected pituitary ACTH-secreting tumor, and 24 hour UFC above the upper limit of normal reference range beyond post-surgical week 6
  - Patients on medical treatment for Cushing's disease the following washout periods must be completed before screening assessments are performed :
    - Inhibitors of steroidogenesis (metyrapone, ketoconazole): 2 weeks
    - Somatostatin analogs (pasireotide): 2 weeks
    - Progesterone receptor antagonist (mifepristone): 2 weeks

- Dopamine agonists (cabergoline): 4 weeks
- CYP3A4 strong inducers or inhibitors: varies between drugs; minimum 5-6 times the half-life of drug

*Exclusion criteria:*

- Patients with compromised visual fields, and not stable for at least 6 months
- Patients with abutment or compression of the optic chiasm on MRI and normal visual fields
- Patients with Cushing's syndrome due to non-pituitary ACTH secretion
- Patients with hypercortisolism secondary to adrenal tumors or nodular (primary) bilateral adrenal hyperplasia
- Patients who have a known inherited syndrome as the cause for hormone over secretion (i.e. Carney Complex, McCune-Albright syndrome, MEN-1)
- Patients with a diagnosis of glucocorticoid-remedial aldosteronism (GRA)
- Patients with cyclic Cushing's syndrome defined by any measurement of UFC over the previous 1 months within normal range
- Patients with pseudo-Cushing's syndrome, i.e. non-autonomous hypercortisolism due to overactivation of the HPA axis in uncontrolled depression, anxiety, obsessive compulsive disorder, morbid obesity, alcoholism, and uncontrolled diabetes mellitus
- Patients who have undergone major surgery within 1 month prior to screening
- Patients with serum  $K^+ < 3.5$  while on replacement treatment
- Diabetic patients whose blood glucose is poorly controlled as evidenced by  $HbA1C > 8\%$

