### *Primary outcome:*

- The primary efficacy outcome will be normalization of mean UFC levels after 4-weeks treatment. This will be measured as the mean of three 24-hour urine specimens collected at baseline and within 5 days before completion of the study. Patients who achieve a mean post-treatment UFC level within the normal range are considered responders.

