### *Secondary outcome:*

- Plasma ACTH, serum cortisol levels will be measured at baseline, day 1, 8, 15, 22 and 29 every 3 hours from 9:00–15:00. The areas under the concentration-time curve (AUC0–8h) for ACTH and cortisol will be calculated using a trapezoidal method from 0–6 h (the last sampling time point) by WinNonlin software (Pharsight, Mountain View, CA). Visual field will be measured at baseline and end of the study.

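### The responder versus non-responder t test on ACTH and cortisol names no variable, time point or baseline adjustment, so milder disease at entry can be mixed with response

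*Combined protocol and SAP*

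**What the plan says.** Section 9.0 (Statistics) plans "The comparison between serum cortisol or plasma ACTH in patients who responded to seliciclib and in those who did not respond". The comparison "in those who did not respond will be performed by a Student's *t* test". The sentence does not say whether the variable is a level, an AUC or a change, or which visit it comes from, and it names no covariate.

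Other parts of the protocol bear on it:

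- **Data available.** Section 7.0, secondary outcome: "Plasma ACTH, serum cortisol levels will be measured at baseline, day 1, 8, 15, 22 and 29 every 3 hours", from 9:00 to 15:00, with AUCs to be calculated. The visit lists in Section 6.0 show the same sampling at the baseline visit and on day 29.
- **Who is a responder.** Section 7.0, primary outcome: "Patients who achieve a mean post-treatment UFC level within the normal range are considered responders".
- **Who can enter.** Section 5.0, inclusion criteria: "Persistent hypercortisolemia established by two consecutive 24 hr UFC levels at least 1.5x the upper limit of normal". No upper limit is given.
- **Where baseline is used.** Section 9.0: "A regression model will be used to investigate the relationship between end-of-study UFC and baseline UFC". No such model is given for ACTH or cortisol.
- **Design rationale.** Section 9.0: "By using subjects as their own controls, we measure pre- and post-treatment changes on the same population". This is not linked to the t test.

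**The concern.** Response is defined by where UFC ends, not by how far it falls. A patient who enters just above the entry limit needs a much smaller fall than one with severe disease, so responders are likely to be the milder patients. If ACTH or cortisol tracks UFC at entry, responders also start lower on those measures. A lower value in responders on day 29 may then only restate where they began.

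The hypothesis in Section 3.0 is that the drug suppresses ACTH production, and this t test is the only test that Section 9.0 names for ACTH. A reader could take a significant result as support for that mechanism when it reflects case mix. Conversely, if the groups happen to start alike, leaving out baseline can leave removable between-patient spread in the error term.

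**Working it through.** **1. The plan's own figure.** For 16 patients and success at 3 or more responders, the exact binomial gives P(X ≥ 3 | 16, 0.05) = 0.0429 and P(X ≥ 3 | 16, 0.25) = 0.8029. The stated one-sided 0.05 and 80% power are reproduced. At the 25% alternative the expected split is 16 × 0.25 = 4 responders and 12 non-responders.

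**2. Why the groups differ at entry.** From k × ULN, the fall needed to reach ULN is 1 − 1/k.

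- Entry limit, k = 1.5: 1 − 1/1.5 = 33%.
- Illustrative severe patient, k = 6: 1 − 1/6 = 83%.

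**3. How the gap carries through.** Suppose post-treatment ACTH depends only on measured baseline ACTH, with pre/post correlation ρ. A baseline gap of g SD then leaves an expected gap of ρ × g SD at the end, with no effect linked to response. For g = 1 and 4 versus 12 patients, simulated rejection rates of a two-sided 5% test (40,000 runs) are:

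| ρ | Expected end gap (SD) | t test on end level | ANCOVA |
|---|---|---|---|
| 0.5 | 0.5 | 12.8% | about 5% |
| 0.7 | 0.7 | 20.5% | about 5% |
| 0.9 | 0.9 | 30.6% | about 5% |

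**4. False positives when the selection itself generates the gap.** The documents give no SD and no correlation for ACTH, so these inputs are assumptions:

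- median UFC 3 × ULN before truncation at 1.5 × ULN;
- log-SD 0.6 for UFC and ACTH;
- UFC halved on average, with log-noise SD 0.35;
- response if post-treatment UFC is at or below ULN;
- pre/post ACTH correlation 0.5 to 0.9;
- no effect on ACTH.

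The mean number of responders over all simulated trials is about 3. Only trials with 3 to 13 responders are analysed, which drops about 40% of runs; the mean among those kept is about 4.

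| Baseline ACTH-UFC correlation | t test on end level | ANCOVA |
|---|---|---|
| 0 | about 5% | near 5% |
| 0.3 | 5-7% | near 5% |
| 0.5 | 7-12% | near 5% |
| 0.7 | 9-21% | near 5% |

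A second simulation, separately coded with response driven by baseline UFC, gave 5.9-8.1%, 7.8-13.1% and 9.6-23.3% at correlations 0.3, 0.5 and 0.7. In it responders started about 0.35, 0.6 and 0.84 SD lower on ACTH.

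**5. Power with balanced baselines.** For a true halving of ACTH in responders (log effect 0.69), in the model of step 4 with zero baseline ACTH-UFC correlation:

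- ρ = 0.3: gain about nil.
- ρ = 0.5: 45.9% for the t test, 53.5% for ANCOVA; 53.5 − 45.9 = 7.6 points.
- ρ = 0.7: 44.4% and 68.4%; 68.4 − 44.4 = 24.0 points.

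A noncentral-t check for a 1 SD difference with 4 versus 12 patients agrees in pattern. The noncentrality is √(4 × 12/16) = 1.73 on 14 df for the t test, and 1.73/√(1 − ρ²) on 13 df for ANCOVA. Power is 36.5% for the t test and 39%, 46% and 61% for ANCOVA at ρ = 0.3, 0.5 and 0.7. This check ignores the cost of chance baseline imbalance, so it slightly flatters ANCOVA.

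**The case against.** **The text does not say that levels are compared.** A reader might infer that the plan discards baseline. The documents do not go that far: Section 9.0 speaks of pre- and post-treatment changes, and the secondary objective in Section 4.0 concerns changes in hormone levels, so a change in AUC could be meant. This stands as a limit on the wording of the point. It does not remove the point, because no change score is stated for this test. A change score is also only a partial answer. With no ACTH effect, ρ = 0.5 and baseline correlations of 0.5 and 0.7, it rejected in 6.9-8.8% of simulated trials. In the 1 SD power check it gained nothing over the end level at ρ = 0.5 (both 36.5%) and was worse at ρ = 0.3 (28%).

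**The size rests on assumptions.** This stands. With uncorrelated baseline ACTH and UFC there is no inflation, and at 0.3 it is small.

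**Power is not always lost.** A reader might infer bias and lost power together. The power figures hold for balanced baselines. When responders start lower, the unadjusted test rejects more often, which is bias.

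**ANCOVA is not a complete cure.** This stands. If the groups differ in a stable underlying level, adjustment for one measured baseline leaves part of the bias: 9.2% rejections against 36% for the end-level t test, at ρ = 0.7 and a 1 SD gap.

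**The comparison is exploratory.** This also stands. It involves about 3 or 4 responders, and no decision depends on it.

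**Conclusion.** The point holds as a minor one on a secondary analysis. Section 9.0 leaves the variable, the time point and the handling of baseline open for its only named ACTH test, while the responder definition and the uncapped entry UFC favour milder patients as responders. If end-of-treatment levels are compared unadjusted, the nominal 5% error is kept at zero baseline ACTH-UFC correlation and rises to 7-12% at 0.5 and 9-21% at 0.7, under the assumptions listed. With balanced baselines, the power given up ranges from about nil to about 24 points at pre/post correlations of 0.3 to 0.7.

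Two stronger readings are not supported. The efficacy conclusion is not at risk, because the 3-of-16 rule uses UFC response only and reproduces as stated. Nor would adjustment turn this test into evidence that seliciclib lowers ACTH: responder status is itself a post-treatment outcome in a single-arm trial, and a fall shared by all patients does not show in a contrast between them.

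**What to change.** In Section 9.0, replace the t test sentence with wording to this effect:

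> Log day-29 plasma ACTH AUC over the six hours sampled (9:00 to 15:00) will be compared between UFC responders and non-responders by ANCOVA, with log AUC from the baseline visit as covariate. The same model will be fitted for serum cortisol. Adjusted responder to non-responder ratios will be given with 95% confidence intervals. Baseline ACTH, cortisol and UFC will be tabulated by responder status. This comparison is exploratory and does not estimate the effect of seliciclib on ACTH.

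The baseline table lets readers judge how much imbalance there was and how much bias may remain. The change needs no new data, visits or patients. It costs one residual degree of freedom (14 to 13 with all 16 patients), which matters only if baseline turns out to predict little.

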### **Section 3.0 Trial objectives and purpose**

**Aim: Evaluate the efficacy and safety of R-roscovitine for treatment of pituitary corticotroph tumors (Cushing disease).**

**Hypothesis: We hypothesize that R-roscovitine will suppress pituitary corticotroph tumor ACTH production and normalize urinary free cortisol levels in patients with Cushing disease.** To date, R-roscovitine has been evaluated in several Phase I and II studies and has shown early signs of anti-cancer activity in approximately 240 patients. Studies included a Phase I study in which single agent seliciclib was administered to patients with advanced non-small cell lung cancer (NSCLC) and two Phase IIa studies in which seliciclib was administered in combination with gemcitabine and cisplatin as first-line treatment and with docetaxel as second-line treatment in NSCLC(26). Seliciclib was also evaluated in a Phase I study in patients with nasopharyngeal cancer (NPC) with evidence of tumor shrinkage and concomitant reduction in copy counts of the EBV virus that is causally associated with the pathogenesis of NPC [IND No. 71,011-CYC202(R-roscovitine or Seliciclib)](27). Results from APPRAISE, a randomized discontinuation, double-blinded, placebo-controlled, Phase IIb study of oral seliciclib capsules as a monotherapy in heavily pretreated patients with NSCLC, demonstrated no difference between the seliciclib and placebo arms in progression free survival but a substantial increase in overall survival was observed (388 versus 218 days respectively (Cyclacel press release Dec 21, 2010). Here, we propose an exploratory, proof of concept clinical trial to determine if seliciclib can safely normalize urinary free cortisol levels by reducing pituitary corticotroph tumor ACTH production in patients with Cushing disease.

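### ACTH and cortisol are related to UFC only through a responder versus non-responder t test, which discards the size of the UFC fall and mixes in baseline severity; a continuous analysis of the same data would be better

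*Combined protocol and SAP*

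**What the plan says.** Section 9.0 lists three secondary analyses. One is a regression of end-of-study UFC on baseline UFC. Another is a Student's t test for "The comparison between serum cortisol or plasma ACTH in patients who responded to seliciclib and in those who did not respond". The third is Fisher's exact test for categorical variables before and after treatment. Only the t test brings ACTH or cortisol together with UFC.

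Section 7.0 (Primary outcome) fixes the grouping: "Patients who achieve a mean post-treatment UFC level within the normal range are considered responders". This is a condition on the final level, not on the change. Entry requires "two consecutive 24 hr UFC levels at least 1.5x the upper limit of normal" (Section 5.0, Inclusion criteria), and no upper limit is stated. A fall of at least 50% that leaves UFC above normal is a separate secondary endpoint in Section 4.0; in the t test such a patient is a non-responder.

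Section 3.0 proposes to find out whether the drug can "safely normalize urinary free cortisol levels by reducing pituitary corticotroph tumor ACTH production". Section 7.0 (Secondary outcome) collects serial ACTH and cortisol at baseline and on days 1, 8, 15, 22 and 29, with AUCs, but names no analysis of them against UFC as a continuous measure.

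The plan does not say whether the t test uses ACTH levels or changes, which time point it uses, or whether it is one- or two-sided. It states no power for this test.

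**The concern.** UFC (a mean of three collections), ACTH and cortisol are all continuous, and all are measured before and during treatment. Cutting UFC at the upper limit of normal has two costs.

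- It treats a patient just above normal like one whose UFC did not move, and it leaves small, unequal groups.
- Ending within normal depends on the starting point as well as on the drug. From 1.5 × ULN the required fall is 1 − 1/1.5 = 33%; from 5 × ULN it is 1 − 1/5 = 80%. A 75% fall from 5 × ULN ends at 1.25 × ULN and counts as non-response.

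At stake is how the trial's evidence on its pituitary hypothesis is read. If changes in ACTH are compared, a real link with the UFC fall is more likely to be missed than it need be. If levels are compared, a difference that reflects milder disease may be taken for a drug effect on ACTH.

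**Working it through.** **Inputs from the plan (Section 9.0).** "We enroll 16 patients"; response rates of 5% (null) and 25% (alternative); success if at least 3 respond; design set "to determine the sample size for 80% power and a one-sided 0.05 significance level".

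**1. The plan's own figure.** With X ~ Binomial(16, p), P(X ≥ 3) = 0.043 at p = 0.05 and 0.803 at p = 0.25. The primary design reproduces.

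**2. Group sizes in the t test.**
- Expected at 25%: 16 × 0.25 = 4 versus 12. At the success boundary: 3 versus 13. At 5%: 0.8 versus 15.2.
- P(X ≤ 1) = 6% at 25% and 81% at 5%. P(X = 0) = 44% at 5%, and then no test can be run.
- With 4 versus 12, a two-sided 5% t test needs a standardised difference of 1.74 for 80% power.

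**3. Information kept by the cut.** For a normal variable split at its lower 25%, the fraction kept is φ(z)²/[p(1 − p)] with p = 0.25, which is 0.54.

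**4. Power if the t test uses ACTH change.** By simulation with n = 16, two-sided 5% and a 25% response rate. The documents give no correlation, SD or baseline distribution, so these are assumed:
- log UFC change and log ACTH change are bivariate normal with correlation rho;
- where baseline varies, log baseline UFC is normal, truncated below at 1.5 × ULN, with median parameter 2.5–4 × ULN and SD 0.5–0.7; the SD of log change is 0.5–0.7.

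| rho | Continuous | t test, cut on change alone | Ratio | t test, baseline also varies | Ratio |
|---|---|---|---|---|---|
| 0.5 | 53% | 29% | 29/53 = 0.55 | 15–23% | 0.28–0.43 |
| 0.6 | 73% | 41% | 41/73 = 0.56 | 19–32% | 0.26–0.44 |
| 0.7 | 90% | 56% | 56/90 = 0.62 | 25–44% | 0.28–0.49 |

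Simulation error moves these by about a point; the lowest cell came out at 14% in a repeat run.

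**5. Sensitivity.** On a wider grid (baseline SD 0.4–0.7, change SD 0.4–0.8) the ratio is 0.21–0.54 for rho 0.5–0.7. At rho 0.8 it is 0.25–0.64 with baseline varying and about 0.74 without. At one-sided 5% it is 0.63–0.74 for the cut alone (rho 0.5–0.7) and reaches about 0.6 with baseline varying. The continuous analysis had more power in every one of these scenarios.

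**6. Who is called a non-responder.** With median parameter 3 × ULN, baseline SD 0.5 and change SD 0.6, the correlation of responder status with log baseline UFC is −0.40, and 33% of non-responders had a UFC fall of at least 50%.

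**7. The other reading: ACTH levels.** Suppose the drug has no effect on ACTH, 25% of patients still normalise UFC, and ACTH level correlates with baseline log UFC at 0.3 / 0.5 / 0.7 (assumed). Over the grid of step 4, the t test finds significantly lower ACTH in responders in about 5–8% / 8–16% / 12–28% of trials, against a nominal 2.5% in that direction.

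**The case against.** A responder comparison is the natural companion to a responder primary endpoint, and the plan never calls it a test of mechanism. Section 3.0 hypothesises that the drug suppresses ACTH and normalises UFC, and Section 4.0 lists hormone changes and levels over time. A reader might infer that an across-patient link between ACTH and UFC is a formal objective; no section says so. That part of the objection stands. The analysis bears on the hypothesis but is not a named aim.

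A reader might also infer that the t test has at most half the power of the alternative. The documents cannot support that as a general statement: the cut alone keeps 55–62%, and the lower figures need assumed baseline variation and a two-sided test.

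Nor do the two harms add up. Loss of power belongs to the reading in changes and spurious differences to the reading in levels; the sentence can mean only one. Under the second reading the ACTH difference is genuine, and the error lies in crediting it to the drug.

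The 5% scenario carries limited weight, since a trial with 0 or 1 responders fails its primary rule anyway. The continuous analysis is itself modest, with 53% power at rho 0.5. In a single arm, spontaneous ACTH fluctuation could also make the two log ratios move together, so it cannot prove mechanism.

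What the objection does not remove is that the planned grouping discards measured information, depends on starting severity, and has a simple replacement.

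**Conclusion.** The point holds as an improvement to a secondary, exploratory analysis. The plan's only analysis joining ACTH or cortisol to UFC rests on a cut that ignores the size of the fall, depends on baseline severity, and gives about 4 versus 12 patients at the 25% rate.

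That the grouping depends on baseline follows from the plan's own definitions. The size of the loss rests on the assumed correlations and spreads: at rho 0.5–0.7 the t test gives up about 24 to 34 percentage points of power from the cut alone (53 − 29 = 24; 90 − 56 = 34), and more if baseline UFC varies as assumed.

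A reader might take this as a flaw in the efficacy conclusion. It is not: the rule of at least 3 responders in 16 does not use this test, and its operating characteristics are as stated.

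**What to change.** In Section 9.0, replace the responder t test with a regression (or Pearson correlation) of each patient's log ratio, end of treatment to baseline, of ACTH AUC on the log ratio of mean 24 h UFC. Do the same separately for cortisol AUC. Include all patients with both values and report the slope or correlation with a 95% CI.

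Name the time points: the day 29 AUC, and the same UFC window as the primary outcome. That window has to be written out, because the visit schedule collects UFC on both days 24–28 and days 30–35. The AUC interval also needs one label, since Section 7.0 names it 0–8 h but computes it over 0–6 h.

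Label the analysis exploratory and supportive, not proof of mechanism. Keep the responder versus non-responder comparison as a descriptive plot or table, and leave the primary rule unchanged.

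The cost is a few lines of text. No new data, visits or patients are needed. The one downside is that a slope on log ratios is less immediate for clinicians than two groups, which the descriptive display offsets.

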**Secondary objectives:**

- To evaluate changes in levels of pituitary hormones and metabolic abnormality; changes in clinical signs and symptoms; changes in tumor size; and safety of seliciclib 400 mg oral administration twice daily for 4 days every week for total of 4 weeks in CD patients.

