**Secondary endpoint:**

- A urinary free cortisol level above the upper limit of the normal range but reduced by  $\geq 50\%$  from baseline at week 4
- Plasma ACTH [ ] hour urinary free cortisol, serum and salivary cortisol levels over time
- Hemoglobin A1C (HbA1C), fasting blood glucose and blood electrolytes, e.g. K+
- Cushing's syndrome clinical signs and symptoms, e.g. weight, body mass index, blood pressure
- Changes in tumor size
- Safety end points: hematologic and blood chemistry including total sodium, potassium, urea, serum creatinine, creatinine clearance, total protein; LFT (ALT, AST, total bilirubin, albumin, ALP, [ ] total cholesterol (TC), LDL-cholesterol, triglycerides; coagulation (PT, INR) and ECG [ ]

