## **Section 7.0 Assessment of Efficacy**

The primary efficacy population will include patients who had baseline mean UFC levels 1.5x above the upper normal range, and who completed the 4-cycle, 4-week treatment period with no more than 2 weeks of interrupted drug doses. Baseline UFC levels are defined as the mean of three 24-hour urine specimens collected within one week of baseline visit.

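### Section 9.0 names no within-patient analysis of plasma ACTH or serum cortisol; its only test for them, responders against non-responders, cannot detect a fall shared by all patients

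*Combined protocol and SAP*

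**What the plan says.** Section 3.0 states the hypothesis that "R-roscovitine will suppress pituitary corticotroph tumor ACTH production and normalize urinary free cortisol levels", and proposes to find out whether the drug can "safely normalize urinary free cortisol levels by reducing pituitary corticotroph tumor ACTH production". The secondary objective in Section 4.0 begins "To evaluate changes in levels of pituitary hormones and metabolic abnormality", and the secondary endpoints include plasma ACTH together with "serum and salivary cortisol levels over time". Section 7.0 schedules ACTH and serum cortisol profiles at baseline and on Days 1, 8, 15, 22 and 29, with an AUC for each. It gives no comparison between visits.

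Section 9.0 names three analyses beyond the primary response rule:

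- a regression of end-of-study UFC on baseline UFC;
- a Student's t test of "serum cortisol or plasma ACTH in patients who responded to seliciclib and in those who did not respond";
- for categorical variables only, a comparison in which they "will be compared in the pre- and post- treatment time points using fisher's exact test".

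Section 9.0 also gives a general design rationale: "By using subjects as their own controls, we measure pre- and post-treatment changes on the same population". That sentence names no variable and no test.

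**The concern.** Responders and non-responders are different patients, so the t test compares two independent groups and cannot be read as a pre/post test. It addresses a fair question: whether normalised UFC goes with lower ACTH. It does not address the one in the hypothesis and the secondary objective: whether ACTH falls from baseline. The plan states an own-control principle and names a pre/post test for categorical variables, but names none for the hormone in its hypothesis.

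Two misreadings are possible. The test could be non-significant although every patient's ACTH fell. It could also be significant although mean ACTH did not change, because response is defined from the post-treatment UFC and may correlate with a patient's underlying ACTH level or with fluctuation late in the study. As no scale (level, change or AUC) or visit is fixed, the analyst would also be choosing among several tests after seeing the data.

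**Working it through.** **The plan's own figure.** With 16 patients and success at 3 or more responders, the exact binomial gives P(X ≥ 3) = 0.043 at a 5% response rate and 0.803 at 25%. The stated one-sided 0.05 level and 80% power are reproduced. The point below does not touch this rule.

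**Inputs.** From Section 9.0: n = 16, response rates of 5% and 25%. The documents give no SD or correlation for ACTH or cortisol, so these are assumed on the log scale: between-patient SD 0.5; within-patient SD σ = 0.15, 0.25 or 0.40. Two-sided 5% tests are also assumed.

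**Why a shared fall cancels.** Write log baseline = u + e0 and log end value = u + e1 + log(1 − f), where f is the shared fractional fall. In the responder minus non-responder difference, log(1 − f) appears in both means and drops out. The pooled SD does not contain it. So t is identical for any f, on log end values and on log changes, given the split. On untransformed end values every observation is multiplied by (1 − f), so t is again unchanged. None of this depends on the assumed SDs.

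**What a paired test sees.** The SD of change is σ√2, the standardised fall is d = |log(1 − f)| / (σ√2), and the noncentrality is d√16. For f = 0.30 and σ = 0.25: d = 0.357 / 0.354 = 1.01, noncentrality 4.04, power 96%.

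| | σ = 0.15 | σ = 0.25 | σ = 0.40 |
|---|---|---|---|
| Paired power, 30% fall | 100% | 96% | 65% |
| Paired power, 20% fall | 98% | 66% | 31% |
| t test, response unrelated to ACTH, any fall | about 5% | about 5% | about 5% |
| Expected 95% CI, true ratio 0.70 | 0.63–0.78 | 0.58–0.85 | 0.52–0.95 |

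Expressed in SDs of change, shared falls of 0.5, 0.8, 1.0 and 1.5 SD give paired power of 46%, 85%, 96% and over 99.9%. The 4 against 12 t test stays near 5% throughout.

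**Simulation with response linked to ACTH** (40,000 trials per setting, σ = 0.25, 25% response, same draws and same split). In 11 correlation settings, t test decisions at 0% and 30% shared fall differed in no trial. The paired test went from 5% to 96% rejection, or to 82% when the size of the fall also varied between patients (SD 0.3).

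**Rejection with no mean ACTH change** (σ = 0.25):

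- t test on log end levels: about 8%, 24% and 74% when response correlates 0.2, 0.5 and 0.9 with underlying ACTH;
- t test on log changes: about 9%, 16% and 29% when response correlates 0.3, 0.5 and 0.7 with end-of-treatment ACTH fluctuation.

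**Dependence on the split** (from the plan's n and rates). At a 5% response rate, P(0 responders) = 0.95^16 = 0.44 and P(1 responder) = 16 × 0.05 × 0.95^15 = 0.37. With none, the test cannot be run. For 80% power the group difference must be 3.11 SD (1 against 15), 2.28 (2 against 14), 1.93 (3 against 13) or 1.74 (4 against 12, the expected split at 25%).

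**The case against.** The strongest reply is that this is an exploratory trial with one formal hypothesis, UFC response. ACTH and cortisol are secondary, carry no decision rule, and descriptive summaries of change are not ruled out. That limits the weight of the point but does not supply the missing analysis.

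A second reply is that nothing in the plan says the t test will be read as evidence of suppression, and that rejecting when response tracks underlying ACTH is a correct detection of association. That is true. The hazard is that it is the only named result for the hormone in the hypothesis, so a reader has nothing else to go on. It is also fair that a real ACTH fall may change who responds, which the primary endpoint would capture, and that the t test can detect a fall that is larger in responders. The cancellation concerns the shared part only.

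Third, Section 9.0 specifies no log transform. On untransformed end levels the no-change rejection rates drop to about 13% and 49% at correlations 0.5 and 0.9. On untransformed changes the cancellation is no longer exact: a 30% shared fall altered the decision in roughly 3% to 7% of trials in most settings tried, and in 10% in the most extreme. The test remains insensitive in practice.

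Fourth, UFC and ACTH come from different days. Section 6.0 collects UFC on Days 24–28 and 30–35, while the last ACTH profile is on Day 29. The assumed correlations with late fluctuation are therefore illustrations only. A related caution stands for the remedy. Drug is dispensed on Days 1, 8, 15 and 22 for four days a week. If each cycle starts at dispensing, which is not stated, the last dosing day is Day 25 (22 + 3), and Day 29 comes after a gap.

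**Conclusion.** The concern holds. Followed as written, Section 9.0 gives no inferential answer to whether ACTH or serum cortisol falls from baseline, and the one test it names cannot give one. The cancellation is algebra and needs no assumed figures. The chance of no responders (44% at a 5% response rate) uses only the plan's n and null rate. The paired power and the no-change rejection rates rest on assumed SDs, correlations and a log scale, and should be read as ranges. The primary 3-of-16 rule is unaffected. This should be corrected before analysis, but it does not threaten the main conclusion of the trial.

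**What to change.** In Section 9.0:

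- Make within-patient change from baseline the main analysis of plasma ACTH and serum cortisol: either a paired comparison of log AUC over 0–6 h, or a repeated-measures model over baseline and Days 8, 15, 22 and 29. Report the Day 29 ratio to baseline with its 95% CI. Describe it as an uncontrolled change from baseline and report the interval since the last dose.
- State the population: all treated patients with data. Note that this differs from the Section 7.0 efficacy set, which requires raised baseline UFC and patients who "completed the 4-cycle, 4-week treatment period with no more than 2 weeks of interrupted drug doses". Show that set as a sensitivity analysis.
- State in advance how the Day 1 profile is used, since Section 6.0 does not say whether it precedes the first dose.
- Keep responders against non-responders as a descriptive comparison, with scale and visit fixed and baseline values shown.
- In Section 7.0, reconcile the AUC label (0–8 h) with the stated 0–6 h calculation.

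The cost is SAP wording and slightly more analysis, with no new samples or visits, plus one more analysis population to report. In a single arm the within-patient change still includes natural fluctuation and regression to the mean, so it cannot by itself attribute a fall to the drug.
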